9.6 Subjects

9.6.1 Inclusion Criteria

The subjects have to meet all of the following criteria to be eligible to participate in the clinical investigation:

- 1. Between 4 to 18 years of age at the time of laceration repair.
- 2. Require suture closure as standard of care for simple straight wounds on trunk or extremities up to 4 cm long.
- 3. Low Tension Laceration, e.g. skin can be easily approximated by pinching with fingers.
- 4. Subject and legal representative(s) are willing and able to comply with the investigational device removal and meet the follow up visit requirements.
- 5. Subject and legal representative(s) have been informed of the nature, the scope and the relevance of the study.
- 6. Subject and legal representative(s) have voluntarily agreed to participation and have duly signed the Informed Consent Form.

9.6.2 Exclusion Criteria

Subjects meeting any of the following criteria will not be permitted to participate in the clinical investigation:

- 1. Known personal or familial history of scar hypertrophy.
- 2. Known or suspected allergies or hypersensitivity to non-latex skin adhesives.
- 3. Atrophic skin deemed clinically prone to blistering.
- 4. Wounds that are easily susceptible to infection because of exposure to unsanitary conditions ("dirty wounds").
- 5. Wounds that require deep dermal closure using sutures.
- 6. Known or suspected mental problems and/or aggressiveness that indicates that the subject might try to take to take the investigational device off.
- 7. Participating in any other clinical investigation.
- 8. Known health condition that would affect healing in the opinion of the investigator.
- 9. Any subject that according to the Declaration of Helsinki is deemed unsuitable for study enrolment.

9.6.3 Number of Subjects

The study population will be comprised of 60 pediatric patients presented to the Pediatric energency department with need of laceration repair, and eligible to study participation according to the inclusion and exclusion criteria. The subjects will be randomly assigned at a 1:1 ratio to either the Zip 4 group (30 subjects) or to the SoC group (30 subjects).

The sample size calculation was based on preliminary data indicating a difference of approximately 30 minutes in wound treatment procedures between the Zip device and SoC sutures. Alpha = 0.05 and power of the test = .9, indicates a sample size of 24 subjects. Assuming 10% dropout rate, the study will include up to 26 subjects. If for any reason the dropout rate should be higher than this, additional subjects might be enrolled in the study to reach a total of 24 completed subjects. Since different areas of the body are being appreciated we will enroll 60 patients.

9.6.4 Methods of Assigning Subjects to the different treatment arms

When the subjects are consented into the investigation they are given a unique three-digit identification number. If the subject is found eligible he/she will be allocated to the next available randomization number, a code of two digits, and the corresponding randomization envelope opened. The envelope contains information on group allocation in accordance with the randomization list. This is not a blinded investigation and both the Investigator and subject will be aware of the group allocation after randomization. The subject's identification number and randomization number will be noted in applicable investigation logs, Case Report Form (CRF) and in the medical journal system for each subject

Subject withdrawal or discontinuation

Subjects and/or legal representatives are free to discontinue participation in the clinical investigation at any time and are not required to give a reason for their decision. However, they that wish to discontinue the investigation should always be asked about the reason(s) for discontinuation and about the presence of any adverse events/adverse device effects and, if possible, be assessed by an Investigator. Discontinuation from the clinical investigation will not affect the future treatment/care of the subject.

If the subject and/or legal representative(s) will withdraw the consent no further data will thereafter be recorded. Data collected up to the date of window and informed consent will be used in the data analysis and for the Clinical Investigation Report (CIR).

Subjects may be withdrawn from the clinical investigation at any time, if deemed necessary by the PI.

Specific reasons for withdrawal of subjects from this clinical investigation are:

- The decision of a subject and/or legal representative(s) to withdraw from the clinical investigation (including if the subject withdraws informed consent).
- The PI deems the subject is unfit for the investigation or suspects' poor CIP compliance.
- Subject is lost to follow-up.

In case of withdrawal, all AEs/ADEs should be followed up. Any questionnaires should be returned by the subject.

In case of subjects lost to follow up; at least 3 documented attempts to reach the subject shall be made prior to categorizing the subject as "lost to follow-up".

Incorrectly enrolled or randomized subjects will be withdrawn from further investigation and assessments. A subject may, however, continue the clinical investigation under exceptional circumstances (i.e. if continuation of investigation or follow up are necessary for the subject's safety and wellbeing, or if only a follow up period remain, and the continuation of the investigation is not expected to be associated with any risk or discomfort for the subject).

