11.9 Missing, unused or spurious data

Spurious data, also known as outliers or mavericks, will be included in the summary tables, though noted in study as abnormal data. Premature withdrawn subject data will also be inclusive to the analysis, as far into the study as possible. Any missing data discovered will be incorporated to the analysis, and noted accordingly.

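### Stopping assessments is the default for incorrectly enrolled or randomised subjects, and an unblinded PI may withdraw on suspicion of non-compliance: day-10 and day-30 outcomes, chiefly the WES, can be lost selectively

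*Protocol*

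**What the plan says.** Two separate rules stand in Protocol section 9.6.4, under the unnumbered subheading on subject withdrawal or discontinuation.

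**Rule A, errors of enrolment or randomisation.** "Incorrectly enrolled or randomized subjects will be withdrawn from further investigation and assessments". The next sentence softens this: "A subject may, however, continue the clinical investigation under exceptional circumstances". One of the listed circumstances is where follow-up is needed for the subject's safety and wellbeing. The other reads "or if only a follow up period remain, and the continuation of the investigation is not expected to be associated with any risk or discomfort". No decision-maker is named.

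**Rule B, withdrawal by the PI.** "Subjects may be withdrawn from the clinical investigation at any time, if deemed necessary by the PI". The specific reasons include "The PI deems the subject is unfit for the investigation or suspects' poor CIP compliance". The same section states: "This is not a blinded investigation and both the Investigator and subject will be aware of the group allocation after randomization". The CRF termination page has a matching box for withdrawal by the Investigator for non-compliance.

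**What continues after withdrawal.** "In case of withdrawal, all AEs/ADEs should be followed up", and questionnaires are to be returned. Section 11.9 adds: "Premature withdrawn subject data will also be inclusive to the analysis, as far into the study as possible". Nothing provides for photographs after withdrawal.

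**The concern.** The closure, and with it the primary endpoint, is done on day 0. An enrolment or randomisation error found after the repair therefore almost always leaves only follow-up to complete. For these subjects the default stops outcome collection, and the case that should be normal is written as exceptional.

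Rule B raises a different problem. The person who decides knows the arm and needs only a suspicion. Compliance is also not symmetric between the arms. The handling restrictions spelled out in sections 5.8 and 9.8.1.1 (petroleum-based ointments, soaking, rubbing, lying on the device) concern the Zip device. Section 9.8.5 says that accidental loss of the device before healing is complete may lead to a less favourable outcome. On the protocol's own account, then, a handling failure can be both a reason to suspect non-compliance and a predictor of a worse result.

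At stake is the randomised comparison of the later outcomes. Blinding the two plastic surgeons does not help if the photographs they would have scored were never taken.

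**Working it through.** **Step 1. Which endpoints can be lost after withdrawal**

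| Endpoint | When collected | Provision after withdrawal |
|---|---|---|
| Closure time (primary) | Day 0 (9.8.3.1) | Already recorded; retained under 11.9 |
| Application VAS | Day 0 (9.8.3.4) | Already recorded; retained under 11.9 |
| Removal VAS | Day 10 | Form handed out at Visit 1 with a self-addressed envelope (9.8.1.1); to be returned (9.6.4) |
| Satisfaction questionnaire | Day 30 | Same |
| WES | Photographs at days 0, 10 and 30, taken by site personnel (9.8.1, footnote 6 to the schedule) | None stated for days 10 and 30 |
| Adverse events | Throughout | Followed up (9.6.4; CRF termination page). Section 17.2 speaks of events ongoing at withdrawal, so questioning for new events is unclear |

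The WES is the one endpoint with no stated route of collection. New adverse events are the second gap. Removal VAS and satisfaction are provided for, although Rule A's wording on assessments sits awkwardly beside that provision.

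**Step 2. Default and exception side by side**

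Rule A uses *will* for stopping and *may* for continuing. The follow-up branch of the exception also requires that continuing is not expected to bring risk or discomfort. The day-10 contact includes removal of the device or sutures, with a pain score, so that condition is not met automatically. Two teams could read the same case in opposite ways.

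**Step 3. Illustrative size**

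The plan has no figure of its own on this point: it gives no rate of incorrect enrolment or of PI withdrawal. The 10% in section 11.5 is overall loss, not loss from one arm. What follows is therefore assumption, not estimate.

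Assume a normal outcome in SD units and no true difference, with a fraction *p* withdrawn from one arm only, being the subjects with the worst outcomes. With z the upper-*p* normal quantile and φ the normal density:

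- Shift in that arm's mean = φ(z)/(1 − p)
- p = 0.10: 0.1755/0.90 = 0.195 SD
- p = 0.20: 0.280/0.80 = 0.35 SD
- If withdrawal correlates only 0.5 with outcome, at p = 0.10: 0.5 × 0.195 = about 0.10 SD

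Standard error of the arm difference, ignoring the subjects lost = √(2/n). The protocol gives conflicting totals (30 in the Synopsis and 9.1, 60 in 9.6.3), so two sizes are shown:

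- n = 30 per arm: √(2/30) = 0.26 SD
- n = 15 per arm: √(2/15) = 0.37 SD

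At p = 0.10 the ratio of shift to standard error is 0.195/0.258 = 0.76 at 30 per arm and 0.195/0.365 = 0.53 at 15 per arm.

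A simulation removed the *k* worst outcomes from one arm (200,000 repeats, two-sided t-test at 5%):

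| Per arm | k | Bias (SD) | Type I error |
|---|---|---|---|
| 30 | 1 | 0.07 | 6.4% |
| 30 | 2 | 0.13 | 9.1% |
| 30 | 3 | 0.19 | 12.6% |
| 15 | 1 | 0.12 | 7.1% |
| 15 | 2 | 0.23 | 10.8% |
| 15 | 3 | 0.33 | 15.9% |

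Three of 30 is 10%, and its 0.19 SD agrees with the formula. The WES is a sum of six binary items, so the normal model is only an approximation.

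**The case against.** The best reply is that the protocol already contains most of the remedy. Rule A's exception covers a subject with only follow-up left, which describes most errors found after the repair. Adverse events are followed up, questionnaires come back, and collected data stay in the analysis. Section 11.3 has a randomisation-based full analysis set (FAS) and a per-protocol set (PPS) in which deviations are handled. Eligibility is checked before the envelope is opened, so incorrect enrolment judged on baseline criteria need not depend on arm. Some post-treatment caution is also legitimate in children: the device or sutures stay on for about 10 days, so it would be wrong to say that withdrawal after day 0 can protect nobody.

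Much of this stands, and it rules out stronger readings that a reader might infer:

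- *That all day-10 and day-30 endpoints are lost, or that the safety comparison is broken.* Section 9.6.4 provides for adverse events and questionnaires.
- *That subjects suspected of poor compliance leave all assessments.* That wording is attached only to incorrectly enrolled or randomised subjects.
- *That the PI decides who was incorrectly enrolled.* Rule A names no decision-maker.

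What the reply does not answer is that the exception is optional, is called exceptional, is conditional on no expected discomfort, and is not written for Rule B. Nor does anything restore the photographs.

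**Conclusion.** The concern holds in a limited form. Followed as written, the two rules *can* cause loss of day-10 and day-30 data related to arm or outcome. The loss falls chiefly on the WES and possibly on new adverse events. Selective loss is a risk, not a stated consequence, and the documents do not show how often it would occur.

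The size of about 0.2 SD, or roughly half to three quarters of a standard error, rests on 10% withdrawal from one arm only and on those subjects having the worst outcomes. Weaker selection gives less: about 0.10 SD at correlation 0.5. The figures show that a handful of subjects could matter in a trial this small; they do not predict the bias.

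The primary endpoint is unaffected for anyone withdrawn after treatment, and no change of sample size follows. This should be corrected because it is avoidable at almost no cost.

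**What to change.** Reword the withdrawal text in section 9.6.4 as follows:

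1. Continued day-10 and day-30 follow-up, including photographs and questioning for new adverse events, is the default for every randomised subject, unless consent is withdrawn or the subject's safety or wellbeing prevents it.
2. Incorrect enrolment, incorrect randomisation and non-compliance are recorded as protocol deviations. They serve only to define the PPS in section 11.3 and are not grounds for stopping assessments.
3. These subjects remain in the FAS in the arm to which they were randomised.

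Align the CRF termination page, which now offers non-compliance as a reason for withdrawal by the Investigator.

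The cost is a wording amendment and a few follow-up contacts that are already scheduled. The safety and wellbeing proviso means that some photographs may still be missing; the reason should then be recorded.

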9.7 Clinical investigation duration

Table 2. Overview clinical investigation duration.

Point of enrolment:	Q2 2018
Estimated enrolment period	5 months
Expected duration of each subject's participation:	30 days
Total expected duration of the clinical investigation:	6 months

9.8 Clinical Investigation Procedures

9.8.1 Schedule of clinical investigation procedures/assessments

The assessments and procedures that will be performed during the clinical investigation are illustrated in *Table 3* below.

Study assessment	Visit 1 Day 0	follow-up 1 Day 10 (+/- 2 days)	follow-up 2 Day 30 (+/- 2 days)
Study information	Х		

Informed consent	Х		
Demographics	Х		
Relevant Medical and Surgical history	Х		
Physical examination (Type, size, location of laceration)	Х		
Inclusion/Exclusion criteria	Х		
Randomization	Х		
Wound preparation, e.g. cleansing ¹	Х		
Local Anesthesia and/or Sedation ²	Х		
Device application ³	Х		
Dressing application	Х		
Study participant instructions ⁴	Х		
Device and dressing removal ⁵		X	
Photographs taken ⁶	Х	X	Х
Visual Analog Scale (VAS)	Х	X	
Wound healing satisfaction questionnaire			X
Subject interview		Х	Х
Adverse event	Х	Х	Х
Medical review / Concomitant medication	Х	Х	Х
Study Exit			Х

¹ According to clinical routine.

² According to clinical routine. Zip group: Anesthesia and/or sedation only use if deemed necessary by Investigator. Document in Concomitant Medication Log.

³ Test group will be treated with Zip 4 device and SoC group with conventional sutures as wound closure.

⁴ Instructions prior discharge regarding post-treatment and additional follow up visits.

⁵ suture ir device removal will be conducted at FU session 1 at the PED or at home by a member of staff of the study

⁶ Photographs will be taken at the wound area during Visit 1 and follow up visits by the site personnel, . Please be aware of not adding any personal numbers or identifying characteristics on the photographs, only subject identification number and visit information.

9.8.1.1 Visit 1 (Screening/Baseline visit)

The Investigator will introduce the clinical investigation and explain the CIP, procedures and objectives to a potential subject and their legal representative(s). The Investigator will verbally inform about the investigation and provide a Patient Information Sheet (PIS) describing the clinical investigation, potential discomforts, risks and benefits of participation. Potential subjects and their legal representatives will be given adequate time for review of the PIS and time to discuss the investigation and ask questions to the Investigator. Any queries that they may have regarding the investigation will be addressed appropriately by the Investigator. Potential subjects and their legal representatives will be instructed that they are free to obtain further information from the Investigator at any time and that they are free to withdraw their consent and to discontinue their participation in the investigation at any time without prejudice.

If the subject and their legal representative(s) are willing to participate in the investigation, they need to sign and date the informed consent form (ICF) together with the Investigator who gave the verbal and written information. The original ICF will be retained in the Investigator Site File (ISF) and a copy provided to the subject and their legal representative(s). The Investigator must obtain written informed consent before any clinical investigation-related procedures are performed, for further details on the informed consent process please see *section 17*.

After written informed consent has been acquired the subject is considered as enrolled. The subject will be allocated to the available subject identification number, a unique three-digit number, used for the identification of the subject in the investigation.

At visit 1 a physical examination of the laceration will be performed, and relevant medical/surgical history collected together with medication review and information on

subject's demographics. After confirmation of the inclusion and exclusion criteria the subject will be randomly assigned to either test or SoC group. Subject randomization procedure will take place in a block randomized fashion where equal numbers of subjects will receive the Zip 4 device and the SoC suture wound closure (1:1 ratio). The randomization will be performed by opening a sealed envelope containing a randomization card, for further details see *section 10.6.4*. The corresponding device written in the opened randomization envelope will be used as laceration repair.

Prior device application the wound will be cleansed, and for SoC subject local anesthesia and/or sedation will be used according to clinical routine. For Zip subjects, local anesthesia and/or sedation only will be used if deemed necessary by the Investigator. Photographs will be taken of the laceration by the study personnel, and thereafter the devices, Zip 4 device or SoC sutures, will be applied as according to the IFUs. After the devices have been applied appropriate, they will be covered with standard of care dressings to provide protection. Thereafter the subject will fill out the Visual Analog Scale (VAS) with assistance from the legal representative(s), if needed.

Prior discharge:

- Post-treatment information of the Zip 4 device or SoC sutures. The subjects and their legal representative(s) in the Zip 4 group will be informed that the subjects may not use ointments containing petroleum as well as reframe from soaking the device during baths or in swimming pools. Furthermore, the subject should not rub or continuously lay on the device since this may weaken the adhesives or damage the device.
- Removal of the Zip 4 device or SoC sutures will be conducted by the a study personnel either at Kaplan Medical Center ER or at the subjects home depending on the subjects preferences.
- The subject and their legal representative(s) will receive verbally and written information regrding the photgraphs that will be taken at day 10 and day 30.
- The subject and their legal representative(s) will receive questionnaires to be filled out at day 10 (VAS) and day 30 (Wound healing satisfaction questionnaire).
- The subject and their legal representative will be given contact information to the site in case of an adverse event or general questions concerning the investigation.
- Follow up visits will be scheduled and the subject and their legal representative(s) will be reminded of the importance of attending. These will be done either at the subjects home or at the Pediatric Emergency Department at Kaplan Medical Center.

During Visit 1 the following assessments/procedures will be performed:

- Demographics
- Relevant medical and surgical history
- Physical examination of the laceration (type, size, location)
- Medication review
- Verification of subject eligibility (check inclusion/exclusion criteria)
- Randomization
- Wound preparation, e.g. cleansing.
- Anesthesia (if required)
- Sedation (if required)
- Photographs taken at the wound prior device application
- Device application
- Dressing application
- VAS
- Study participant instructions: hand out Zip device removal instructions and photograph instructions

- Hand out questionnaires (VAS and Wound healing satisfaction questionnaire) and selfaddressed envelopes to be filled out in conjunction with the telephone follow up 1 and 2.
- Telephone follow ups scheduled

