4 INTRODUCTION

4.1 Background

Every year a significant number of lacerations are managed at the Pediatric Emergency Room (1). Lacerations require proper skin closure in order to heal properly with good cosmetic outcome. Sutures are a common method for laceration closure [2]. With proper preparation of the wound, skilled procedure and compliant post-procedure wound care, outcomes tend to be favorable with good cosmetic outcome. Nevertheless, suturing takes significant time and may require a high degree of skill and experience [3]. The application of sutures may require multiple injections of anesthesia into the wound site, which may cause anxiety in patients, particularly in children [4]. For a child, the thought of needles and sutures may be worse than the actual injury itself. In some cases, pediatric patients may require sedation to reduce anxiety. In the patient-centered health care, it is a matter of course to increase patient satisfaction. One step in this direction might be to replace suturing with non-invasive methods.

According to current clinical routines, suturing should in most cases be performed by physicians [5]. It therefore takes significant resources (time and personnel) to treat a laceration. From diagnosis, consultation, anesthesial injections and sedation (if required) until suturing, it can take more than one hour. Pediatric emergency departments often have a stressful environment with many patients to treat and it would be valuable if this process could be shortened. In addition, treated children may prefer to remove the sutures at a clinic even if it is usually not required with a follow up visit. This additional visit takes time for the medical staff, the child and the parent/guardian. Hence, a faster and more efficient treatment might reduce time and resources, allowing more patients to be treated at the Emergency departments.

ZipLine Medical, Inc. has developed a novel, non-invasive skin closure device called "Zip Surgical Skin Closure Device" (Zip device) as an alternative to conventional sutures, staples and glue for closure of the skin for surgical incisions or laceration repair. The Zip device is a single use, sterile medical device that is designed to provide closure speed superior to sutures, while resulte in a suture-like cosmetic outcome [6]. Feedback from post-market surveillance and evidence from published clinical studies suggest that these design intentions are correct [7].

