9.1 General

This is a prospective, randomized, controlled post-market clinical investigation to compare the use of Zip 4 device to standard of care skin closure sutures in pediatric subjects requiring laceration repair. 30 subjects will be recruited

The investigation consists of one screening/baseline visits at day 0 and 2 follow ups at day 10 and day 30 (*Figure 4*). After written informed consent has been acquired at the screening/baseline visit the subject will be evaluated and checked for eligibility by a pediatric emergency physician with clinical experience and expertise in laceration repaiar . An eligible subject will be randomized (1:1) to either test or SoC group. Subjects in the test group will be treated with the Zip 4 device, and subjects in the SoC group will instead be treated with conventional sutures as wound closure. After treatment, the subject is scheduled for follow up 10 days and 30 days post-treatment. At day 10 follow up study personnel will remove the Zip device or sutures. During both follow up calls at day 10 (after removal of device) and day 30, the subjects are assessed for the outcome of the laceration repair though subjects interviews and questionnaires filled out by the subject with help of their legal representative(s), if necessary. In addition, a blinded panel of 2 independent plastic surgeons will evaluate the cosmetic outcome of the laceration repair by reviewing digital photographs taken at screening/baseline visits versus 10 days and 30 days follow up.

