9.3 Secondary endpoints (performance)

- Difference in Wound Evaluation Score at 10 days and 30 days post-treatment compare to baseline when comparing scar satisfaction and appearance of the subjects receiving Zip 4 Surgical Skin Closure Device versus Standard of Care closure suturing. The score will be based on digital photographs taken on day 0, day 10 and day 30 and made by an independent panel of blinded two specialists in plastic surgery.
- Rate of wound healing satisfaction in subject at 30 days post-treatment when comparing Zip
 4 Surgical Skin Closure Device versus Standard of Care closure suturing. The endpoint will
 utilize a questionnaire for the subject when possible or his caretakers to fill out.
- The level of pain in connection to device application and removal measured by a visual analog scale (VAS) 0-100 mm.

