11.2 Sample size

Sample sizes for the two treatment groups of Zip 4 device and SoC suture, were determined, and based on prior studies performed for the primary endpoint of mean times for incision closure time. The justification for sample sizes determined, is based on the following delta differences, and pooled Standard Deviation (SD) calculations for mean time differences of closure methods.

Differences and variances are based on prior data, with a delta difference of 30 mins, pooled SD = 22, alpha error = .05, power of the test = .9, the sample size determined for each grouis 12, or 24 subjects total. In consideration is a possible 10% loss calculation, a total maximum number of up 26 subjects or up to a maximum of 13 subjects per group is determined.

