- 11. Any subject that according to the Declaration of Helsinki is deemed unsuitable for study enrolment.

ELIGIBILITY CONCLUSION

Does the Subject fulfill all the inclusion- and none of the exclusion criteria? *If* **NO** – *please terminate subject.*

YES

🗌 NO

Date (DD-MMM-YYYY): _____ Investigator signature:

גרסה 1 מתאריך 12/1/18

VISIT 1 (Randomization)

ALLOCATION OF RANDOMIZATION NUMBER TO SUBJECT		
The subject has been allocated the following Randomization Number: _		
ALL OCATION OF TREATMENT		

The subject has been allocated to the following treatment group

Zip 4 device

SoC sutures

VISIT 1 (Post-randomization)

PHOTOGRAPHS TAKEN	
Photographs taken prior laceration repair	NO YES
If NO , please clarify:	

LACERATION REPAIR PROCEDURE			
Start Time of preparation of procedure	_ _ : _ : _ HH:MM:SS		
Time of registration to the PED	_ _ : _ : _ HH:MM:SS		
Wound cleaning			
Start Time of wound cleaning: _ _ : _ : _ : _ HH:MM:SS	Stop Time of wound cleaning: _ _ : _ .		
Cleaning method (mark all that applies):	Sterile water Soap Removal of debris Other:		
Was anesthesia required for wound cleaning? If YES , please fill out Concomitant Medication Log.	□ NO □ YES		
Was sedation required for wound cleaning? If YES , please fill out Concomitant Medication Log.	□ NO □ YES		
Wound closure			
Was anesthesia required for wound closure?	NO YES, please specify:		
If YES , please fill out Concomitant Medication Log.	No new anesthesia used, anesthesia applied during cleaning was adequate.		
	New or additional anesthesia required for wound closure.		
Was sedation required for wound closure?	NO YES, please specify :		
If YES , please fill out Concomitant Medication Log.	 No new sedation used, sedation applied during cleaning was adequate. New or additional sedation required for wound closure. 		
Number of 7in 4 deviace word:			
Number of Zip 4 devices used: (ONLY APPLICABLE FOR ZIP GROUP)	□ 1 □ 2 □ 3 □ 4 □ Other: □ N/A		

Subject ID No	Randomization
No	

Wound dressing used on the device:	Mepore Other:
Stope Time of procedure, i.e. after wound dressing been applied.	_ _ : _ : _ HH:MM:SS
Time of PED Discharge	_ _ : _ : _ HH:MM:SS

VAS - Visit 1 Has the subject completed the VAS form? VAS Score _____ If NO, please provide reason:

ADVERSE EVENT/ADVERSE DEVICE EFFECT QUESTION		

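### The day-0 photograph that serves as the Wound Evaluation Score baseline is taken after randomisation, and section 9.8.1.1, unlike the CRF order, places it after anaesthesia given under an arm-dependent rule

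*Protocol*

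**What the plan says.** Protocol 9.3 defines the endpoint as "Difference in Wound Evaluation Score at 10 days and 30 days post-treatment compare to baseline", compared between arms. Section 9.1 has a blinded panel of two plastic surgeons "reviewing digital photographs taken at screening/baseline visits versus 10 days and 30 days follow up". The day-0 photograph is thus the reference for every change score. The CRF scores it on the same six binary items as the later photographs: step-off, contour irregularity, width, edge inversion, inflammation and overall cosmesis.

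The Visit 1 narrative in 9.8.1.1 first randomises the subject by envelope. It then cleanses the wound and states that "for SoC subject local anesthesia and/or sedation will be used according to clinical routine", whereas Zip subjects receive anaesthesia or sedation only where the investigator finds it necessary. The photograph comes next: "Photographs will be taken of the laceration by the study personnel, and thereafter the devices, Zip 4 device or SoC sutures, will be applied". The Visit 1 procedure list in the same section keeps this order.

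The CRF places the item "Photographs taken prior laceration repair" on the page headed Visit 1 (Post-randomization), ahead of the repair-procedure block in which cleaning, anaesthesia and sedation are recorded.

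Section 9.6.4 says that the trial is not blinded and that the investigator knows the allocation once the subject is randomised. Section 9.5 allows local anaesthesia as injection or gel, and section 4.1 notes: "The application of sutures may require multiple injections of anesthesia into the wound site".

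**The concern.** Randomisation makes the arms equal in expectation only on what is measured before allocation can influence it. This baseline is recorded afterwards, by site staff in an open-label trial. On the wording of 9.8.1.1 it also follows an intervention that the protocol intends to use differently in the two arms. Several scored items, inflammation and contour in particular, describe how the tissue looks at that moment, and an injection or gel at the wound could plausibly change them.

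If that happens, the arms start from different reference scores for reasons unrelated to the scar. A change-from-baseline comparison would read this as a difference in cosmetic result. The fault cannot be repaired once the photographs have been taken.

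**Working it through.** **The plan's own figures.** The protocol gives no SD, effect size or sample size for the WES. Its only calculation, in 11.2, concerns closure time: "with a delta difference of 30 mins, pooled SD = 22, alpha error = .05, power of the test = .9". With the usual two-sided formula, n per arm = 2 × (1.960 + 1.282)² × (22/30)² = 2 × 10.51 × 0.538 = 11.3, rounded up to 12, or 24 in total, as stated. This point does not touch that figure.

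**Order of the day-0 steps, side by side.**

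| Source | Order given | Photograph relative to randomisation | Photograph relative to anaesthesia |
|---|---|---|---|
| 9.8.1.1, narrative | randomise, cleanse, anaesthesia/sedation, photograph, device | after | after |
| 9.8.1.1, Visit 1 list | randomise, wound preparation, anaesthesia, sedation, photograph, device | after | after |
| CRF, Visit 1 (Post-randomization) | photograph item, then repair block with cleaning, anaesthesia, sedation | after | before |
| Table 3 in 9.8.1 | day only | not given | not given |

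Every source that gives an order puts the photograph after randomisation. They disagree on whether it precedes anaesthesia. The CRF records no time for the photograph, so practice could vary from subject to subject without trace.

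**How a baseline difference enters the endpoint.** Let Y0 be the day-0 score and Yt the day-10 or day-30 score (0 to 6, higher is better). Then:

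Zip minus suture difference in mean change = (mean Yt, Zip − mean Yt, suture) − (mean Y0, Zip − mean Y0, suture).

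The second bracket has expectation zero if Y0 is measured before allocation. Suppose instead that anaesthesia before the photograph lowers Y0 by k points, and that shares pS (sutures) and pZ (Zip) are photographed after it. The second bracket then has expectation k × (pS − pZ), and the comparison shifts by that amount in favour of sutures. If k is negative, the shift favours Zip. Using Y0 as a covariate does not remove the problem, because a fraction of the same arm difference is still subtracted.

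**Illustration.** None of these inputs is in the documents. Assume k between 0.5 and 1.0 point and pS − pZ between 0.25 and 0.75:

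- low: 0.5 × 0.25 = 0.125 points
- middle: 0.5 × 0.50 = 0.25 points
- high: 1.0 × 0.75 = 0.75 points
- k = 0, or photograph before anaesthesia in all subjects: 0 points

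**The case against.** The case against giving this much weight is substantial.

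- **The CRF order.** If sites work down the CRF, the photograph precedes cleaning and anaesthesia, and this route to bias closes. That is correct. It makes the timing relative to anaesthesia an unresolved conflict rather than a settled fact, but the photograph still follows randomisation.
- **Anaesthesia is not fixed by arm.** Zip subjects may receive it, the Visit 1 list makes it conditional for everyone, it may be a gel, and sedation alone has no evident effect on a photograph. This stands. What differs by arm is the rule, and the resulting difference in use is unknown.
- **The mechanism is not documented.** Nothing in the protocol says that anaesthesia changes a WES item. An open wound that needs suturing may already score near the floor in both arms, leaving little to lose. This also stands, and k could be small or zero.

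Two stronger readings are tempting. A reader might infer that the panel could recognise the arm from signs of anaesthesia on day 0. The documents do not support this: the wound is unclosed in both arms at that point, either arm may have been anaesthetised, and nothing says that the signs are visible in a photograph. A reader might also turn the shift into a false-positive rate. That would need an SD that the protocol does not give and a significance test that it does not name for the WES; 11.1 names t tests for the stated hypothesis and for the VAS.

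**Conclusion.** The point holds in limited form. The WES baseline is not a pre-randomisation measurement under any part of the protocol that gives an order. Section 9.8.1.1 further places it after anaesthesia given under an arm-dependent rule, and the CRF contradicts that placement. Bias in the change-score comparison is possible but not shown. It requires that anaesthesia alters the scored appearance, that its use before the photograph differs between arms, and that sites follow 9.8.1.1 rather than the CRF. Size and direction cannot be derived from the documents; the range of 0.125 to 0.75 points is an illustration under assumed inputs. One secondary endpoint is affected. The primary endpoint, closure time, and its sample size are not.

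**What to change.** In 9.8.1.1, in both the narrative and the Visit 1 list, place the day-0 photograph with the physical examination of the laceration: after consent, before the envelope is opened and before any anaesthesia. Move the CRF photograph item to the pre-randomisation pages so that the two agree.

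The cost is one reordered step and one moved CRF item, with no extra visit. Two small drawbacks follow: the wound may be photographed before full cleansing, though equally in both arms, and some children who then fail screening will have been photographed.

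If the order cannot be changed, compare the day-10 and day-30 scores directly between arms for all subjects, without subtracting the day-0 score. Do not discard baselines subject by subject according to whether anaesthesia came first. That could remove more of them in the suture arm and would mix raw scores with change scores in proportions that depend on treatment.
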